13.0 Risks to Subjects

Risks associated with TMS and MRI.

Challenges will include patient tolerability to TMS, the MRI scanner, and the study clinical and neurocognitive assessments. The primary safety concern, the same as that for conventional once-daily rTMS, is risk of seizure. However, all reported TMS-induced seizures during conventional or accelerated protocols have been self-limiting, and NONE required further intervention to stop the seizure; no post-seizure sequelae or recurrent seizures developed. Extensive precautions with regard to suicidal ideation/homicidal ideation risk will be followed.

Due to the novel nature of the proposed study, Table 4 is included to provide a representative range of the stimulation parameters and populations examined with accelerated rTMS. The dosing range of these studies covers the range proposed in this study. In these as well as other accelerated rTMS studies, the authors have demonstrated the safety, feasibility and acceptability of accelerated, high-dose studies of rTMS in neurologically intact samples. Of pertinence to the issue of safety as well as the conceptual model proposed here, Holtzheimer et al.⁸¹ showed reliably enhanced neuropsychological performance on the Repeatable Battery for the Assessment of Neuropsychological Status (RBANS) from baseline to six weeks after an accelerated, high-dose rTMS protocol in patients with major depression. Furthermore, Baeken et al.^{82,83} as well as Herremans et al.⁸⁴ and Williams et al.⁸⁵ additionally collected structural and functional imaging and demonstrated no adverse changes pre- to post-accelerated rTMS. Taken together, these studies demonstrate that the potential risks of accelerated rTMS are likely similar to conventional once-daily rTMS.

Table 4 . Representative accelerated rTMS studies for neuropsychiatric conditions.

Study	Total Pulses	Days	Total # Sessions	Stimulation Intensity	Disorder	Frequency	N
Holtzheimer et al. ⁸¹	15,000	2	15	100%	Major Depression	10 Hz; 5s train, 25s ITI	14
Baeken et al. ^{82,83}	31,200	4	20	110%	Major Depression	20 Hz; 1.9s train; 12s ITI	15
Herremans et al. ⁸⁴	31,200	3	15	110%	Alcohol Use Disorder	20 Hz; 1.9s train; 12s ITI	19
Desmyter et al. ⁹²	32,400	4	20	110%	Major Depression	54 bursts of three; 2s train; 8s ITI s	50
Duprat et al. ⁹³	32,400	4	20	110%	Major Depression	54 bursts of three; 2s train; 8s ITI s	50
[name] et al. ⁸⁶	54,000	3	9	120%	Suicidal ideation	10 Hz;	41
McGirr et al. ³⁴	60,000	10	20	120%	Major Depression	10 Hz; 5s train, 25s ITI	27

Modirrousta et al. ⁹⁴	90,000	3	30	110%	Major Depression	10 Hz; 5s train, 25s ITI	18
Williams et al. ⁸⁵	90,000	5	10	90%	Major Depression	54 bursts of three; 2s train; 10s ITI	7
Schulze et al. ⁹¹	120,00 0- 180,00 0	10-15	20-30	120%	Major Depression	20 Hz; 2.5s train; 10s ITI	65

Weighing potential risks related to TMS. Based on previous clinical applications of left prefrontal rTMS in depression and in various other psychiatric disorders, as well as risks published by researchers and communicated experiences, it is hypothesized that left prefrontal rTMS (as proposed) is likely to be effective in enhancing cognition. This study is an important necessary step to characterize the safety, feasibility, efficacy and also durability of the proposed quality of life enhancing effect.

Potential worsening of neuropsychiatric symptoms with TMS. Several studies have thus far demonstrated the feasibility of using rTMS in depression without any indicators of exacerbation of symptoms. The research team will work closely with participants to familiarize them with the nature of this experimental setup. All staff will also be trained to be alert to any emergence of neuropsychiatric symptoms and/or psychosocial impairment. An ethical issue concerning the use of variable doses was considered at length; however, this concern is made easier by understanding that all participants will be given an active course of rTMS. Thus, even the lowest doses have previously shown efficacy in treating depression and may improve cognition among healthy participants in the study 1. Additionally, all participants will be assessed throughout each day for emerging side effects.

Potential changes in cognitive function. There have been no reports of deleterious changes (more than a minute) in cognitive function (memory, attention, etc.) in rTMS studies. Safety studies specifically looking for these changes did not find any effects of rTMS. Holtzheimer et al.⁸¹ showed reliably enhanced neuropsychological performance on the Repeatable Battery for the Assessment of Neuropsychological Status (RBANS) from baseline to six weeks after an accelerated, high-dose rTMS protocol in patients with major depression. This study will assess for potential changes in cognitive function with pre- and post-treatment cognitive batteries designed to look for potential TMS effects, if they exist.

Potential hearing loss. The discharge of the rTMS coil generates a high-energy click that may cause cochlear damage. Humans exposed to rTMS have shown temporary increases in auditory threshold (especially at high frequencies) lasting at least 5 minutes and less than 4 hours⁸⁹. Foam earplugs can protect against these changes and will be worn by the patients and researchers present during TMS sessions. Due to high dosage delivery in this proposal, participants will be instructed to ensure proper fit of earplugs prior to each session.

Safety in case of pregnancy. This protocol will exclude pregnant and breastfeeding women (women of child bearing age will undergo a pregnancy test prior to enrollment).

Risk of facial twitching and skin irritation. The TMS coil can cause facial twitching, skin irritation, or both, which can be acutely unpleasant. This typically often reduces over the course of treatment. Additionally, all patients will have a foam insert placed between the coil and their scalp for comfort and this typically reduces this discomfort. Furthermore, facial twitching and skin irritation are typically only acute and subside with the end of stimulation.

Risk of a first-degree burn. The TMS coil can heat up during use. The machine used in this study has two major protective engineering features: (1) an external heat monitor that will shut down the system if the coil gets too warm; and (2) a liquid-coiled coil design that keeps the coil much cooler than previous models. Additionally, all patients will have a foam insert placed between the coil and their scalp for comfort and also to act as additional thermal protection. The TMS treater will periodically monitor coil temperature during each treatment.

MRI risks. Exposure to magnetic field strengths used in the present study is not shown to be a significant health risk. Risks to an unborn fetus from exposure to the MRI field strength used in the proposed research (3 Tesla) are unknown. Therefore, pregnant females and those who may become pregnant (unwilling to follow study restrictions limiting chances of conception) will not be allowed to participate. Participants will be asked to lie still and awake for 30 minutes in the scanner and this can occasionally result in soreness, stiff back, etc. Participants will be queried approximately every 10 minutes about their comfort. The main risk associated with MR imaging is the possibility of introducing metal to the magnet or its close proximity. Participants are thoroughly screened to prevent metal being brought into the MR environment. Other potential hazards of MRI scanning include: collision hazards, noise, neurostimulation at rapid sampling

rates (i.e., short TRs), body temperature changes, helium, and nitrogen hazards. The MRI facility is tested regularly by internal and external safety monitoring teams. These risks are minimal, and the facility is run within FDA guidelines. All investigators and research assistants running participants in the Center for Biomedical Imaging are thoroughly trained in MR safety as a requirement to run scans.

Risks associated with the parabolic flight (ZERO-G Experience®).

Injury or Illness. There is risk of injury or illness from sudden changes in gravity, altitude and/or turbulence, and could include physical contact of one's body with the interior of the aircraft and other participants during weightlessness, as well as objects and liquids floating in the aircraft. There is the danger of property damage, personal injury or illness (minor or serious) and/or death resulting from weightlessness, the conduct of the ZERO-G Experience®, flight malfunction or mechanical failure and/or anything else related to the ZERO-G Experience®. The risks of such Injuries & Damages are involved in such high adventure programs as the ZERO-G Experience® and subjects may have to exercise extra care for their own person and for others around them in the face of such hazards and that despite exercising such care Injuries & Damages may occur.

Hazards and Risks Unforeseen and Foreseen. This experience involves exposure to a variety of hazards and risks foreseen and unforeseen, which are inherent in or may result from each ZERO-G Experience® and some of which cannot be eliminated without destroying the unique character of the ZERO-G Experience®.

Lack of Medical Personnel. There may not be rescue or medical personnel on board the aircraft to address and treat the Injuries & Damages to which the participants (subjects and study team personnel) may be exposed to as a result of the ZERO-G Experience®. However, [name] will be aboard the flight and all Zero-G personnel are trained in basic life support and cardiopulmonary resuscitative equipment is available on the plane.

Nausea or Vomiting due to Motion Discomfort. Motion discomfort can lead to nausea or vomiting. During the preflight training, the ZERO-G Experience® staff will provide some useful tips on in-flight movements that will help participants to reduce their chance of motion discomfort. Unlike the astronauts in training, the flyers will experience 30 parabolas, which is enough to provide a pleasurable experience but not enough to cause motion discomfort. An often-made mistake by flyers is not eating prior to the flight. ZERO-G provides a flight- friendly meal and encourages all participants to eat before and during the preflight training. Flying on an empty stomach is not recommended and can aid in creating motion discomfort.

The Zero-G Experience Risks of Other Persons. Injuries & Damages can occur by natural causes or activities of other persons, other participants, the Mission Director and Coaches, assistants, the study team personnel, or other third parties, as a result of negligence, the conduct of the ZERO-G Experience® or because of other reasons.

Decompression and Loss of Consciousness. While the probability of an explosive decompression on the ZERO-G aircraft is similar to any other Part-121 operation, commercial airplane operation, the implications of not getting oxygen into the body immediately could be significant including permanent brain damage or death.

Unknown Risk of Performing single pulse TMS during Parabolic Flight

Subjects will be exposed to TMS during parabolic flight for at most 40 seconds. However, as TMS has previously not been performed in a microgravity environment, all risks associated with TMS during parabolic flight cannot be known. Microgravity may result in unknown altered cerebral physiology which may alter the response to TMS and it is for this reason that study arm 3 is being performed.

Nevertheless, the investigators have taken several precautions to reduce the chance that a subject would be exposed to any serious risks from combined TMS and parabolic flight:

- First and foremost, only single pulse TMS will be performed. As discussed above, the risk of seizure induction with TMS is related to the intensity, duration, frequency and rest interval of stimulation. For study arm 3, only single pulse TMS will be performed such that TMS pulses will be spaced 1 second apart.
- The intensity of TMS will be very low. The intensity will be set to be at most just above the amount needed to cause a brief thumb twitch.
- The subjects will be exposed to a small number of TMS pulses (at most 40 TMS pulses total during parabolic flight)
- The duration of exposure to TMS during parabolic flight will be very brief. During parabolic flight, resting motor threshold will be determined. This will take at most only approximately 40 seconds total per subject.
- [name] will be present on the flight and in constant observation of the subjects. At any sign of an adverse event requiring medical attention, they will notify Zero-G flight personnel who will inform the pilot to end the parabolic flight maneuvers and return to the airport to get medical treatment for the subject. 911 will be called and emergency personnel will meet the team at the airport.

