To assess the biological efficacy of TMS during microgravity, we will determine resting motor threshold (rMT) in 10 subjects before, during and following parabolic flight (sessions 1-3). To determine rMT, we will briefly apply single pulse TMS. We will use a standard clinical algorithm (adaptive parameter estimation by sequential testing) to determine rMT of the abductor pollicis brevis muscle in an automated fashion. The measurement takes 20 seconds to perform (20 stimuli using single pulse TMS)^{75,76}.

Pre-flight data collection: First, on the ground pre-flight, the optimal location for stimulus induction will be identified. This location will be marked on the scalp in order to facilitate quick and reproducible identification of this site during the in-flight and post-flight sessions. At this location the TMS coil will be fixed firmly in place and the rMT will be determined. The subjects will also undergo a 10 minute standard computerized cognitive battery (WinSCAT) used by NASA to assess cognitive function in astronauts during International Space Station flights⁶⁰.

In-flight data collection: The in-flight rMT measurement will be performed by placing the coil in the same location identified pre-flight. The coil will be secured in place using stabilization hardware developed with Zero-G similar to the fixation hardware in use in our lab. The flight profile includes 30 parabolas each with approximately 25 seconds of microgravity. This will allow up to 2-3 in-flight measurements per subject providing a margin for human error.

Post-flight data collection: The same procedure will also be utilized to obtain the post-flight measurement. The subjects will also undergo a computerized cognitive battery (WinSCAT) post-flight.

Any significant change (based on established values in normal controls⁵⁴) in rMT during flight compared with pre- and post-flight values will be interpreted as an indicator of an altered physiological response to TMS during microgravity.

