[figure not shown]
Research activities during parabolic flight

Upon entering the aircraft, subjects and the research team will be directed to an area in the back of the plane which contains standard aircraft seating. Subjects and the research team will remain in this area during take-off and flight until the aircraft reaches an appropriate altitude. The subjects and research team will stay seated until signaled by Zero G personnel that it is time to move to the section of the plane where all experimental procedures will take place. At that time, the parabolic portion of the flight will begin.

For each parabola, Zero-G personnel provide the study team with adequate notice that the microgravity portion of the flight is approaching. This gives the research team time to get the subject in place in preparation for the upcoming TMS application. During TMS, the subject will be seated in a chair fixed to the floor of the aircraft and wear a seatbelt. (See the figure). The TMS coil will be securely fixed in place using an adjustable arm attached to the chair. The subject will place his/her head in a chin rest and forehead rest attached to the chair. The subject will hold their head against the TMS coil for the 20 seconds of TMS. One member of the research team will start the software which will control application of the TMS pulses and ensure the subject's head is in the appropriate position against the TMS coil. Another member of the research team ([name] or [name]) will closely monitor the subject for any discomfort or adverse event. After the 20 seconds of TMS, the subject will move from the experimental set up to the nearby designated location where subjects remain when not actively involved in the study as the research team prepares the next subject for the next parabola.

During parabolic flight, go-pro cameras will be used to video record the study.

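### Arm 3: the methods offer up to three in-flight motor-threshold measurements per subject, but the stated safety maximum covers only two full ones (minor inconsistency)

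*Combined protocol and SAP*

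**What the plan says.** Section 9.0 (Study Design / Methods, Study Arm 3) gives the size of one measurement: "The measurement takes 20 seconds to perform (20 stimuli using single pulse TMS". It describes the flight in these terms: "The flight profile includes 30 parabolas each with approximately 25 seconds of microgravity". From that it concludes: "This will allow up to 2-3 in-flight measurements per subject providing a margin for human error".

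The part of section 9.0 on research activities during the flight sets out a single turn. "One member of the research team will start the software which will control application of the TMS pulses". Then: "After the 20 seconds of TMS, the subject will move from the experimental set up to the nearby designated location", while the team prepares the next subject for the next parabola. Nothing in section 9.0 mentions a per-subject maximum number of pulses.

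Section 13.0 (Risks to Subjects, on the unknown risk of single pulse TMS during parabolic flight) states the maximum three times:

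- in its opening line: "Subjects will be exposed to TMS during parabolic flight for at most 40 seconds";
- in the list of precautions: "at most 40 TMS pulses total during parabolic flight";
- in the next precaution, on duration: "This will take at most only approximately 40 seconds total per subject".

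**The concern.** The upper end of the range in the methods does not fit under the maximum in the risk section. Section 13.0 offers the small pulse count and short exposure as precautions, on the ground that TMS has not been done in microgravity before and its risks there are not fully known. A limit given for that reason should agree with the procedure it limits.

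The methods present the extra measurements as slack for mistakes. The third slot is therefore most likely to be used after an attempt has gone wrong, which is when pulses already delivered have to be counted. If a subject had two full runs and then a third, as the wording of section 9.0 permits, the team would exceed the limit it set itself in section 13.0.

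**Working it through.** **Inputs**

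| Quantity | Value | Source |
|---|---|---|
| Pulses per measurement | 20 | Section 9.0, Study Arm 3 |
| Time per measurement | 20 s | Section 9.0, Study Arm 3 |
| In-flight measurements per subject | up to 2-3 | Section 9.0, Study Arm 3 |
| Parabolas; microgravity in each | 30; about 25 s | Section 9.0, Study Arm 3 |
| Subjects | 10 | Sections 5.0 and 9.0 |
| Maximum pulses per subject in flight | 40 | Section 13.0 |
| Maximum time per subject in flight | about 40 s | Section 13.0 |
| Pulse spacing | 1 s | Section 13.0 |

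**Step 1. Reproduce the safety maximum.** Exposure = number of full measurements × 20 pulses (20 s).

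- One: 1 × 20 = 20 pulses, 20 s. Within the limit.
- Two: 2 × 20 = 40 pulses, 40 s. Exactly the limit.

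The section 13.0 figures therefore correspond to two full measurements.

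**Step 2. Reproduce the range in the methods.** A window of about 25 s holds one 20 s run, so one parabola gives one measurement. Parabolas per subject = 30 / 10 = 3, assuming one flight with every parabola usable. This matches the top of the 2-3 range.

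**Step 3. Compare the two.** Three full measurements: 3 × 20 = 60 pulses and 3 × 20 = 60 s. Excess over the limit: 60 − 40 = 20 pulses, and 20 / 40 = 50%. The time excess is likewise 20 s, or 50%.

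**Step 4. Check that rounding does not explain the gap.** Twenty pulses spaced 1 s apart span 19 s from first to last. On that count the 40 s limit holds 40 / 19 = 2.1 measurements, still only two full ones. The pulse limit gives 40 / 20 = 2 in any case.

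**Step 5. When does a full run in a third parabola fit?** It needs 20 pulses, so earlier in-flight attempts must have delivered no more than 40 − 20 = 20 in total. After one full run (20 pulses) and one attempt stopped after k pulses, the remaining allowance is 40 − 20 − k = 20 − k:

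- k = 0 (slot lost before any pulse): 20 remain, and a full run fits.
- k = 1: 19 remain, one short of a full run.

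So the third slot is usable for a full run in some circumstances, but not in general.

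**The case against.** The strongest reply is that the two sections answer different questions. Section 9.0 says how many measurements the flight profile has room for; section 13.0 says how much stimulation a subject will receive. A spare slot need not be used, and one can be lost with no pulse delivered, for instance if the subject is not in position in time. Two full measurements satisfy both sections, and the word total in section 13.0 already counts pulses from aborted attempts. On this view the governing limit is explicit, and section 9.0 merely fails to repeat it.

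Much of that stands. Section 9.0 does not commit to a third measurement, so the plan does not require a breach. But the capacity reading reconciles the sections only under a condition that section 9.0 leaves out, and section 9.0 calls the extra slots measurements, each of which it has defined as 20 stimuli. At the upper end of the range, one of the two figures needs correcting.

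It is also fair to reply that 20 further single pulses, near threshold and 1 s apart under constant observation, are a small addition. The documents do not show that 40 pulses marks a risk threshold; it may simply describe two planned measurements. The point here is consistency with a stated precaution, not a claim of harm.

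Three stronger readings are tempting and should be set aside:

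- **A flight-wide excess.** A reader might multiply up to 10 × 60 = 600 pulses against 10 × 40 = 400. The limit is per subject, so this total has no bearing on it, and it would need all 30 parabolas used with none lost, which removes the slack the extra slots are meant to provide.
- **Staff will not know the limit.** A reader might infer this because section 9.0 omits it. Both sections are in the same document, and section 9.0 puts physicians experienced in TMS and assistants trained in its safe use on the flight. Nothing suggests that they would overlook section 13.0.
- **Damage to the Arm 3 result.** The power calculation in the Statistical Plan rests on 10 subjects and on session-to-session variability of motor threshold. It does not use the number of in-flight repeats.

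**Conclusion.** The inconsistency is real and minor. The limit of 40 pulses and about 40 s covers two full measurements; a third would take that subject to 60 pulses and about 60 s, 50% over. This rests on the plan's own definition of a measurement as 20 stimuli in 20 s, and it arises only if the upper end of the 2-3 range is used with full runs, or if a full run follows earlier attempts totalling more than 20 pulses. The estimate of three slots per subject further assumes a single flight with every parabola usable; the 50% figure does not depend on it.

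The other precautions (single pulses, low intensity, constant observation) hold either way. The correction is worth making before the flight because it concerns a stated human-exposure limit, but nothing in the scientific design turns on it.

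**What to change.** **Preferred.** In the in-flight data collection paragraph of section 9.0, state that each subject receives at most two full in-flight measurements (40 pulses in total, per section 13.0), and that a third parabola may be used only if cumulative in-flight pulses, including those from aborted attempts, stay at or below 40. For a full run, that means 20 or fewer pulses already delivered. Cost: one or two sentences, and one fewer full repeat per subject than the present upper figure.

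**Alternative, if three full measurements are truly intended.** Restate the three figures in section 13.0 as 60 pulses and about 60 seconds (the opening time limit, the pulse limit and the duration precaution). Cost: three figures, and a slightly less favourable stated exposure.

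Either way, the endpoint, sample size and analysis stay as they are.
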